	(Day Relative to C1D1)		Cycle 1				Cycle 2		Cycle 3-n	801	802	803	804-X	
			(±3 days)				(±3 days)		(±3 days)	30 day follow-up ±5 days	60 day follow-up ±5 days	90 day follow-up ±5 days	Q90D	
Procedure	≤28	≤7	D1	D2	D8	D15	D1	D2	D1					
														Radionuclide bone scans should be performed only for patients with mCRPC. See Section 8.1.3.
Tumor assessment-measurement of palpable and/or visible lesions	X		See Instructions							See Instructions				See Section 8.1
Whole blood (PK)			See Section 1.3.1.											See Section 8.5.
Urine (PK)			See Section 1.3.1.											See Section 8.5.
Serum (Pharmacodynamics)			See Section 1.3.1.											See Section 8.6.
Whole Blood (PGx)			See Section 1.3.1.											See Section 8.8.
Plasma			See Section 1.3.1.							See Section 1.3.1.				See Section 8.8.
Serum (Biomarkers)			See Section 1.3.1.											See Section 8.8.
Whole Blood (CTCs)	See Section 1.3.1		See Section 1.3.1							See Section 1.3.1				For mCRPC patients only. Samples to be taken every 3 weeks. See Section 8.8.
Tissue	See Section 1.3.1		See Section 1.3.1.											See Section 8.8., 8.8.1.
Patient dosing diary			X											

Baseline, On-Study and Post-Study Treatment Follow-up SoA													
	Baseline		Cycle = 21 days						Short-Term Follow Up a			Long-Term Follow-Up b	Instructions
	(Day Relative to C1D1)		Cycle 1			Cycle 2		Cycle 3-n	801	802	803	804-X	
			(±3 days)			(±3 days)		(±3 days)	30 day follow-up ±5 days	60 day follow-up ±5 days	90 day follow-up ±5 days	Q90D	
	≤28	≤7	D1	D2	D8	D15	D1	D2	D1				
Procedure													
Administer LY3475070			X										See Section 6.1
Administer pembrolizumab (for patients assigned to combination treatment)			X				X		X				See Section 6.1

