#### **9.4.3.2. Secondary Analyses**

The **disease control rate** (DCR), defined as the proportion of patients who achieved a CR or PR or SD) out of all patients treated, will also be summarized. Best response is determined from a sequence of responses assessed. Two objective status determinations of CR before progression are required for a best response of CR. Two determinations of PR or better before progression, but not qualifying for a CR, are required for a best response of PR.

**Duration of response** (DoR) is defined as the time from the date measurement criteria for CR or PR (whichever is first recorded) are first met until the first date that disease is recurrent or objective progression is observed, per RECIST v1.1 criteria, or the date of death from any cause in the absence of objectively determined disease progression or recurrence. Duration of SD will be calculated only for patients with best response of SD. It is measured from the date of start of treatment to the date of first progression of disease or the date of death due to any cause, whichever is earlier. For each patient who is not known to have died or to have had a progression of disease as of the data-inclusion cut-off date, duration of SD will be censored at the date of last objective response assessment prior to the date of any subsequent systemic anticancer therapy.

**Progression-free survival** (PFS) is defined as the time from the date of start of treatment to the first date of the observed clinical or radiologically documented PD or death due to any cause,

whichever occurs first. For patients who are not known to have died or progressed as of the data-inclusion cut-off date, PFS time will be censored at the date of the last objective progression-free disease assessment prior to the date of any subsequent systematic anticancer therapy.

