### PFS Event/Censoring Scheme

Situation a	Event/Censor	Date of Event or Censor
Tumor progression or death	Event	Earliest date of PD or death
No tumor progression and no death	Censored	Date of last adequate tumor assessment per RECIST v1.1, or date of first dose (whichever is later) b
Unless		
No baseline radiologic tumor assessment available	Censored	Date of first dose
No adequate postbaseline tumor assessment available and death reported after 2 scan intervals following the first dose b, c	Censored	Date of first dose
Tumor progression or death documented immediately after 2 or more scan intervals following last adequate tumor assessment or randomization (whichever is later) b, c	Censored	Date of last adequate tumor assessment, per RECIST v1.1, or date of first dose (whichever is later) b
New therapeutic anticancer treatment started prior to tumor progression or death	Censored	Date of last adequate radiological assessment prior to new therapeutic anticancer therapy b

Abbreviations: CR = complete response; PD = progressive disease; PFS = progression-free survival; PR = partial response; RECIST v1.1 = Response Evaluation Criteria in Solid Tumors; SD = stable disease.

- a Symptomatic deterioration (i.e., symptomatic progression that is not confirmed per RECIST v1.1) will not be considered as tumor progression.
- b Adequate tumor assessment per RECIST v1.1 refers to an assessment with one of the following responses: CR, PR, SD, or PD.
- c Refer to the statistical analysis plan for the definition of 2 scan intervals, including any adjustment for scan window.

**Time to response (TTR)** is defined as the time from the date of start of treatment to the date measurement criteria for confirmed CR or PR (whichever is first recorded) are first met. For patients who are not known to have achieved CR or PR as of the data-inclusion cut-off date, TTR will be censored at the date of the last objective disease assessment prior the date of any subsequent systematic anticancer therapy.

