Abbreviations: CR = complete response; PD = progressive disease; PFS = progression-free survival; PR = partial response; RECIST 1.1 = Response Evaluation Criteria in Solid Tumors, Version 1.1; SD = stable disease.

^a Symptomatic deterioration (ie, symptomatic progression that is not confirmed per RECIST 1.1) will not be considered as tumor progression.

^b Adequate tumor assessment per RECIST 1.1 refers to an assessment with one of the following responses: CR, PR, SD, or PD.

^c Refer to the statistical analysis plan for the definition of 2 scan intervals, including any adjustment for scan window.

Time to response (TTR) is defined as the time from the date of start of treatment to the date measurement criteria for confirmed CR or PR (whichever is first recorded) are first met. For patients who are not known to have achieved CR or PR as of the data-inclusion cut-off date, TTR will be censored at the date of the last objective disease assessment prior the date of any subsequent systematic anticancer therapy.

Exploratory Endpoints

As the exploratory objective, the efficacy parameters based on iRECIST will also be analyzed.

Overall response rate (iORR) is measured by the percentage of patients who achieved a complete response (iCR) or partial response (iPR) as their best overall response (iBOR) out of all

treated patients (safety population). The best overall response (iBOR) is defined as the best response across all time point assessments based on RECIST 1.1 and iRECIST.

Progression-free survival (iPFS) should be the date of randomization (the date of first dose for single arm study) to the date at which progression criteria are first met (ie, the date of first iUPD) provided that iUPD or a sequence of consecutive iUPD is confirmed by an iCPD, or the iUPD followed by only iUPDs at subsequent assessments, or no more tumor assessments, or to the death date from any cause in the absence of progressive disease. Patients known to be alive and without the iUPD as mentioned above as of the data inclusion cut-off date for a particular analysis will be censored at the time of the last adequate tumor assessment (a detailed iPFS event/censoring scheme is provided in the table below).

iPFS Event/Censoring Scheme

Situation ^a	Event/Censor	Date of Event or Censor
iUPD confirmed at next assessment (iCPD), or Consecutive iUPD followed by an iCPD	Event	(First) iUPD date

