iUPD followed by only iUPD at subsequent assessments and no further tumor assessment available.	Event	First iUPD date of the consecutive iUPDs
iUPD without subsequent assessment	Event	iUPD date
Death	Event	Death date if no iUPD date as in the above 3 situations before death.
No Death and no iUPD or iUPD is followed by iSD/iPR/iCR/	Censored	Date of last adequate tumor assessment per iRECIST, or date of randomization (first dose for single arm study) (whichever is later) ^b
Confirmed iUPD (including all the first 3 Event cases) or death reported after 2 scan intervals following the last adequate tumor scan	Censored	Date of last adequate tumor scan prior to Confirmed IUPD (iCPD) or Death.
No baseline radiologic tumor assessment available	Censored	Date of randomization (first dose for single arm study)
No adequate postbaseline tumor assessment available and death reported after 2 scan intervals following the first dose ^{b, c}	Censored	Date of randomization (first dose for single arm study)

iPFS Event/Censoring Scheme

Abbreviations: “i” indicates immune responses assigned using iRECIST. iCR = complete response; iPR = partial response; iSD = stable disease; iUPD=unconfirmed progression; iCPD=confirmed progression.; iPFS = progression-free survival; RECIST = Response Evaluation Criteria in Solid Tumors;

^a Symptomatic deterioration (ie, symptomatic progression that is not confirmed per iRECIST) will not be considered as tumor progression.

^b Adequate tumor assessment per iRECIST refers to an assessment with one of the following responses: iCR, iPR, iSD, iUPD, or iCPD.

^c Refer to the statistical analysis plan for the definition of 2 scan intervals, including any adjustment for scan window. (new anti-cancer therapy in SAP)

Duration of response (iDoR) is defined as the time from the date measurement criteria for iCR or iPR (whichever is first recorded) are first met until the first date that disease is recurrent or objective progression (as assessed by investigators) is observed, or the date of death from any cause in the absence of objectively determined disease progression or recurrence. Patients known to be alive and without disease progression as of the data inclusion cut-off date for a particular analysis will be censored at the time of the last adequate tumor assessment. iDoR will follow the same censoring scheme as iPFS. iDoR will be analyzed for the treated patients who achieve iCR/iPR as the best of overall response (iBOR).

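### The PFS definition counts clinical progression while its event table excludes it, with no precedence stated; the TTR censoring rule would inflate a Kaplan-Meier response curve

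*Protocol*

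**What the plan says.** **PFS definition.** Protocol 9.4.3.2 and SAP 6.7 use the same sentence: PFS runs from start of treatment to "the first date of the observed clinical or radiologically documented PD or death due to any cause".

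**PFS event/censoring table.** Footnote a hangs on the heading of the Situation column, so it covers every row. The Protocol has "Symptomatic deterioration (i.e., symptomatic progression that is not confirmed per RECIST v1.1) will not be considered as tumor progression"; the SAP repeats it as "Symptomatic deterioration (ie, symptomatic progression that is not confirmed per RECIST 1.1) will not be considered as tumor progression". Footnote b adds: "Adequate tumor assessment per RECIST v1.1 refers to an assessment with one of the following responses: CR, PR, SD, or PD". If new therapy starts before progression or death, the censoring date is "Date of last adequate radiological assessment prior to new therapeutic anticancer therapy". Every other censoring row gives the first dose as the date or as a fallback; this one does not.

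**Surrounding text.** The objective that lists PFS (Protocol Section 3) specifies investigator assessment by RECIST v1.1. The DoR definition uses objective RECIST progression, and the PFS censoring sentence refers to objective assessments. The SAP's iPFS runs to "the date at which progression criteria are first met (ie, the date of first iUPD" and carries its own exclusion: "Symptomatic deterioration (ie, symptomatic progression that is not confirmed per iRECIST) will not be considered as tumor progression". The Schedule of Activities has a row "Tumor assessment-measurement of palpable and/or visible lesions", which is one possible meaning of *clinical*.

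**mCRPC.** Protocol 8.1.3 applies RECIST only where disease is measurable. It defines progression by bone scan and, for non-measurable disease, by a confirmed PSA rise. Inclusion criterion 11 admits mCRPC patients without measurable disease.

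**TTR.** In both documents, patients without a known CR or PR are censored at their last objective assessment. A best response of CR or PR needs two determinations before progression. Protocol 9.4.1 and SAP 6.7 put efficacy analyses on treated patients. SAP 6.7 assigns Kaplan-Meier to time-to-event parameters through an open list of examples that does not name TTR.

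**The concern.** Two programmers working from the same plan can derive different PFS events for the same patient. The disagreement concerns event status as well as date, and it arises when a patient is deteriorating, so censoring there is likely to be informative and to push PFS upward. The path is foreseeable: Protocol 7.1 has patients stop treatment if they need another effective agent for any reason, and Protocol 8.1.1 ends follow-up imaging once subsequent therapy begins. The study is open label, so an unsettled rule could be settled after results are visible.

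For TTR, a patient who has progressed or died can no longer produce a qualifying response. Censoring that patient tells Kaplan-Meier that the patient was still able to respond later. One minus the Kaplan-Meier estimate then exceeds the proportion who respond and may disagree with the reported ORR.

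**Working it through.** The documents give no event count, power or precision for PFS or TTR, so there is no plan figure to reproduce for these endpoints. The nearest figure is the Clopper-Pearson table in Protocol 9.2. Its row for 10 of 40 recomputes to 0.127 to 0.412, matching the stated 0.13 to 0.41. It is used below only as a scale for sampling error.

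**Single-patient traces** (assumed histories, 9-week scan schedule from Protocol 8.1.1)

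| History | Definition | Table |
|---|---|---|
| SD Week 9, clinical PD Week 14, new therapy Week 15 | Event, Week 14 | Censored, Week 9 |
| SD Week 9, clinical PD Week 14, no new therapy, RECIST PD Week 18 | Event, Week 14 | Event, Week 18 |
| Clinical PD Week 6, new therapy Week 7 | Event, Week 6 | New-therapy row gives no date |

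A fourth case concerns mCRPC: no measurable disease, alive, PSA rise at Week 12 confirmed at Week 15. Section 8.1.3 calls this progression. If RECIST is applied only to measurable disease, the patient has no adequate assessment under footnote b and the table censors at first dose.

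**Group effect on PFS** (all inputs assumed). Exponential PFS with median m of 13 or 18 weeks, read at Week 27 (three scan intervals). A share c of progressions is clinical only, with new therapy before the next scan.

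- Progression probability per interval: q = 1 − exp(−ln 2 × 9/m). This is 0.381 for m = 13 and 0.293 for m = 18.
- Definition: (1 − q)³ = 0.237 and 0.354.
- Table: a share c of each interval's progressors is censored at the preceding scan, giving [(1 − q)/(1 − qc)]³.

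| Median | Definition | Table, c = 5% | c = 10% | c = 15% |
|---|---|---|---|---|
| 13 weeks | 23.7% | 25.1% | 26.6% | 28.3% |
| 18 weeks | 35.4% | 37.0% | 38.7% | 40.5% |

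The shift runs from 1.4 points (25.1 − 23.7) to 5.1 points (40.5 − 35.4). At m = 13, the number reclassified by Week 27 is N × (1 − 0.237) × c: about 0.8, 1.5 and 2.3 patients of 20, or 1.5, 3.1 and 4.6 of 40. The formula treats first-interval cases as censored at first dose, which is the fallback missing from the new-therapy row. At m = 13 those are 0.381/0.763, about half of the reclassified patients.

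**TTR by Kaplan-Meier in all treated patients** (assumed: N = 20, 4 responders, 16 non-responders all progressed or dead and censored; doubling every count gives the same values)

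- Responses 4/0/0 at Weeks 9/18/27: 1 − 16/20 = 0.200 under any censoring pattern.
- Responses 3/1/0, censored 8/4/4: 17/20 × 8/9 = 0.756, so 1 − KM = 0.244. With censoring 4/4/8 it is 0.215; with 12/2/2 it is 0.320.
- Responses 2/1/1, censored 8/4/4: 18/20 × 9/10 × 4/5 = 0.648, so 1 − KM = 0.352. With censoring 4/4/8 it is 0.257; with 12/2/2 it is 0.500.

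The true proportion is 0.20 in every case.

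**The case against.** **The footnote plainly governs.** It covers the whole table, the table is the operational rule, and the objective, DoR and iPFS all point the same way. If *clinical* means measured palpable or visible lesions, the conflict disappears. This carries weight on which reading was probably intended. It does not supply precedence: no sentence does so, and none defines *clinical*.

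**The TTR method and population are given.** A reader might infer that the plan names neither. The documents do not support that: the all-treated population is stated in Protocol 9.4.1 and SAP 6.7, and the Kaplan-Meier list is open. What remains is that TTR is not named in the list, and that applying those general rules to the stated censoring produces the overstatement. It is also fair that ORR with its exact interval is the planned response probability, and that nothing says one minus Kaplan-Meier will be reported as one.

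**The new-therapy row is covered elsewhere.** A patient with no scan, no progression and no death also fits the general no-event row, which has the first-dose fallback. A reader should therefore not conclude that the table as a whole yields no date. However, the new-therapy row is listed as an exception to the general row, and read alone it gives none.

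**mCRPC is a different question.** True in origin: Amendment (d) added Section 8.1.3, and the SAP, based on Protocol (a), could not reflect it. The unreconciled text is in current Protocol 9.4.3.2, and the same edit can settle it.

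**Conclusion.** The PFS inconsistency is real, stands in both documents and has no stated precedence, although the weight of the text favours the footnote. The TTR rule, combined with the general Kaplan-Meier and all-treated rules, overstates cumulative response when some responses come after the first scan; if all come at the first scan there is no bias.

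The size is modest. On assumed shares of 5 to 15% and medians of 13 or 18 weeks, PFS at Week 27 shifts by about 1 to 5 points. That compares with an interval about 28 points wide for 10 of 40. The documents give no basis for these shares or medians, and a larger share would give a larger shift. The TTR figures depend on the assumed timing of responses and censoring.

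A reader might infer that the trial's main conclusions are at risk. The documents do not support that. PFS is secondary in both phases and TTR in Phase 1b, and no test is named for either. ORR, DLTs, the sample size and the no-response enrolment rule in Protocol 9.5 are untouched. The new-therapy row and the mCRPC link are secondary clean-ups. The point should be corrected before analysis.

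**What to change.** In Protocol 9.4.3.2 and SAP 6.7:

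1. In the PFS definition, replace the clinical-or-radiological wording with *objectively documented PD per RECIST v1.1 (including measured palpable or visible lesions)*.
2. Give the new-therapy row the same later-of-first-dose fallback as the general no-event row.
3. Reconcile footnote b with Protocol 8.1.3 for mCRPC patients without measurable disease. State whether bone-scan and confirmed PSA progression are PFS events, whether the first or the confirming date is used, and which of these assessments count as adequate.
4. Delete the TTR censoring sentence and summarise TTR descriptively in confirmed responders (n, median, range), leaving ORR as the response probability.

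The cost is wording only, with no new data. A sensitivity analysis counting clinical progression as an event is optional and may not be derivable. Discontinuation reasons are collected and summarised in predetermined categories, but the documents do not show clinical progression as a category of its own.

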### PFS Event/Censoring Scheme

Situation a	Event/Censor	Date of Event or Censor
Tumor progression or death	Event	Earliest date of PD or death
No tumor progression and no death	Censored	Date of last adequate tumor assessment per RECIST v1.1, or date of first dose (whichever is later) b
Unless		
No baseline radiologic tumor assessment available	Censored	Date of first dose
No adequate postbaseline tumor assessment available and death reported after 2 scan intervals following the first dose b, c	Censored	Date of first dose
Tumor progression or death documented immediately after 2 or more scan intervals following last adequate tumor assessment or randomization (whichever is later) b, c	Censored	Date of last adequate tumor assessment, per RECIST v1.1, or date of first dose (whichever is later) b
New therapeutic anticancer treatment started prior to tumor progression or death	Censored	Date of last adequate radiological assessment prior to new therapeutic anticancer therapy b

Abbreviations: CR = complete response; PD = progressive disease; PFS = progression-free survival; PR = partial response; RECIST v1.1 = Response Evaluation Criteria in Solid Tumors; SD = stable disease.

- a Symptomatic deterioration (i.e., symptomatic progression that is not confirmed per RECIST v1.1) will not be considered as tumor progression.
- b Adequate tumor assessment per RECIST v1.1 refers to an assessment with one of the following responses: CR, PR, SD, or PD.
- c Refer to the statistical analysis plan for the definition of 2 scan intervals, including any adjustment for scan window.

**Time to response (TTR)** is defined as the time from the date of start of treatment to the date measurement criteria for confirmed CR or PR (whichever is first recorded) are first met. For patients who are not known to have achieved CR or PR as of the data-inclusion cut-off date, TTR will be censored at the date of the last objective disease assessment prior the date of any subsequent systematic anticancer therapy.

### 9.4.3.3. Tertiary/Exploratory Analyses

Overall survival (OS), as well as the efficacy parameters based on iRECIST will also be analyzed as the exploratory objectives. The definition of efficacy endpoints based on iRECIST will be described in the SAP.

**Overall survival** is defined as the time from the first start of study treatments until death from any cause. If the patient is alive, lost to follow-up, or withdrawn from study at the time of data analysis, OS data will be censored on the last date the patient is known to be alive.

### 9.4.4. Safety Analyses

All patients who receive at least 1 dose of any study therapy will be evaluated for safety and toxicity.

The MedDRA Version 22.0 (or higher) will be used when reporting AEs by MedDRA terms. The MedDRA Lower Level Term (LLT) will be used in the treatment-emergent computation. Treatment-emergent adverse events will be summarized by System Organ Class (SOC) and by decreasing frequency of Preferred Term (PT) within SOC.

Safety analyses will include summaries of the following:

- DLTs at each DL in the dose escalation phase and DLT-equivalent AEs for expansion cohorts;
- AEs, including severity and possible relationship to study drug;
- SAEs, including possible relationship to study drug;
- AEs leading to dose adjustments;
- discontinuations from study treatment due to AEs or death;
- treatment emergent abnormal changes in laboratory values;
- treatment emergent abnormal changes in vital signs and ECGs.

### 9.4.5. Pharmacokinetic/Pharmacodynamic Analyses

Selected PK descriptors for LY3475070 (based on actual sampling times), including  $C_{max}$ , approximate time of  $C_{max}$  ( $t_{max}$ ), and AUC will be calculated by noncompartmental analysis methods and/or model simulations. As an exploratory analysis, PK descriptor estimates for trough concentrations ( $C_{min}$ ) at steady state following repeated dose may be evaluated.

In addition, PK parameter estimates for LY3475070 as single agent and in combination with pembrolizumab may be calculated, data allowing. The version of any software used for the analysis will be documented, and the program will meet the Lilly requirements of software validation. It is possible that other validated, equivalent PK software programs may be used if appropriate, warranted, and approved by Global PK/pharmacodynamics management.

PK/pharmacodynamics analyses may be conducted to explore exposure-response relationships between LY3475070 concentrations in systemic circulation and various pharmacodynamic measures as second step if dose-response relationship is positively assessed.

Renal clearance of LY3475070 will be calculated as the ratio of amount excreted/AUC from time 0 to time t ( $AUC_{0-t}$ ), and will be compared with unbound glomerular filtration rate,

estimated using creatinine renal clearance and plasma unbound fraction ( $F_u$ ) ( $F_u \times$  amount of creatinine excreted/creatinine  $AUC_{0-t}$ ).

